**6.1.6 Evaluation of target lesions by RECIST v1.1**

Complete Response (CR): Disappearance of all target lesions. Any pathological lymph nodes (whether target or non-target) must have reduction in short axis to  $<10$  mm.

Partial Response (PR): At least a 30% decrease in the sum of the diameters of target lesions, taking as reference the baseline sum diameters.

Progressive Disease (PD): At least a 20% increase in the sum of the diameters of target lesions, taking as reference the smallest sum on study (this includes the baseline sum if that is the smallest on study). In addition to the relative increase of 20%, the sum must also demonstrate an absolute increase of at least 5 mm. (Note: the appearance of one or more new lesions is also considered progressions).

Stable Disease (SD): Neither sufficient shrinkage to qualify for PR nor sufficient increase to qualify for PD, taking as reference the smallest sum diameters while on study.

**6.1.7 Evaluation of Non-Target Lesions by RECIST v1.1 (excluding bone lesions, which will be assessed as below)**

Complete Response (CR): Disappearance of all non-target lesions and normalization of tumor marker level. All lymph nodes must be non-pathological in size ( $<10$  mm short axis).

Note: If tumor markers are initially above the upper normal limit, they must normalize for a patient to be considered in complete clinical response.

Non-CR/Non-PD: Persistence of one or more non-target lesion(s) and/or maintenance of tumor marker level above the normal limits.

Progressive Disease (PD): Appearance of one or more new lesions and/or *unequivocal progression* of existing non-target lesions. *Unequivocal progression* should not normally trump target lesion status. It must be representative of overall disease status change, not a single lesion increase.

Although a clear progression of “non-target” lesions only is exceptional, the opinion of the treating physician should prevail in such circumstances, and the progression status should be confirmed at a later time by the review panel (or Principal Investigator).

**6.1.8 Evaluation of bone disease based on Radionuclide bone scans by PCWG3:**  
Changes in intensity will not be used as an outcome measure.

Stable or Improved: A stable or improved classification requires that no new lesions appear on radionuclide bone scan or that new pain has not developed in an area that was previously visualized.

Progression (Non-Response): Appearance of two or more new skeletal lesions that is confirmed on a repeat scan. An increase in the size or intensity of known skeletal lesions will not be considered progression.

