#### **6.1.2 Disease Parameters by RECIST V1.1**

Measurable disease. Measurable lesions are defined as those that can be accurately measured in at least one dimension (longest diameter to be recorded) as  $\geq 20$  mm by chest x-ray, as  $\geq 10$  mm with CT scan, or  $\geq 10$  mm with CT scan, MRI, or calipers by clinical exam. All tumor measurements must be recorded in millimeters (or decimal fractions of centimeters).

*Note: Tumor lesions that are situated in a previously irradiated area should not be considered measurable unless they have demonstrated progression.*

Malignant lymph nodes. To be considered pathologically enlarged and measurable, a lymph node must be  $>15$  mm in short axis when assessed by CT scan (CT scan slice thickness recommended to be no greater than 5 mm). At baseline and in follow-up, only the short axis will be measured and followed.

Non-measurable disease. All other lesions (or sites of disease), including small lesions (longest diameter  $<10$  mm or pathological lymph nodes with  $\geq 10$  to  $<15$  mm short axis), are considered non-measurable disease. Bone lesions, leptomeningeal disease, ascites, pleural/pericardial effusions, lymphangitis of skin or lung, inflammatory breast disease, and abdominal masses (not followed by CT or MRI), are considered as non-measurable.

*Note: Cystic lesions that meet the criteria for radiographically defined simple cysts*

*should not be considered as malignant lesions (neither measurable nor non-measurable) since they are, by definition, simple cysts.*

*'Cystic lesions' thought to represent cystic metastases can be considered as measurable lesions, if they meet the definition of measurability described above. However, if non-cystic lesions are present in the same patient, these are preferred for selection as target lesions.*

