**For Patients with Non -Measurable Disease (i.e., Non Target Disease)**

Non-Target Lesions	New Lesions	Overall Response
CR	No	CR
Non-CR/non-PD	No	Non-CR/non-PD*
Not all evaluated	No	not evaluated
Unequivocal PD	Yes or No	PD
Any	Yes	PD

\* 'Non-CR/non-PD' is preferred over 'stable disease' for non-target disease since SD is increasingly used as an endpoint for assessment of efficacy in some trials so to assign this category when no lesions can be measured is not advised

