## 6.3 Assessment of secondary endpoints

- 6.3.1 The safety and tolerability of sEphB4-HSA in patients with mCRPC will be assessed according to NCI CTCAE v 5.0 and reported by the toxicity, severity, and attribution will be recorded for each cycle.
- 6.3.2 The time to PSA progression will be assessed by calculating the interval from administration of the first dose of drug on cycle 1 day 1 to PSA progression. PSA progression is defined by the criteria in section 6.1.5 PSA will be assessed every odd cycle.
- 6.3.3 The overall response rate will be the proportion of patients with measurable disease who received at least 1 dose of the study drug and as their best response achieved a partial or complete response (responder). A subject will be classified as a responder if the RECIST 1.1 criteria for a CR or PR are satisfied (see 10.1.6 and 10.1.7) as well as the absence of confirmed progression on bone scan assessed by PCWG3 (see 10.1.8) at any time up to and including the defined analysis cut-off point. Disease evaluation will be assessed by imaging at baseline and 2 months after starting therapy; thereafter, imaging will be conducted every 3 months. After 1 year, imaging can be done every 4 months for patients with stable disease or better. Scans may also be conducted at any time, if clinically indicated.

6.3.4 The time to radiologic progression (rPFS) will be assessed by calculating the interval from administration of the first dose of drug on cycle 1 day 1 to the time to radiologic progression by RECIST 1.1 or PCWG3 bone criteria (10.1.6-108) or death from any cause. Imaging will occur at baseline and 2 months after starting therapy; thereafter, imaging will be conducted every 3 months. After 1 year, imaging can be done every 4 months for patients with stable disease or better. Scans may also be conducted at any time, if clinically indicated.

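### The bone exclusion is not carried into the new-lesion rules of 6.1.6 and 6.1.9, so one unconfirmed new bone lesion can be scored as an rPFS event although 6.1.8 does not count it as progression

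*Combined protocol and SAP*

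**What the plan says.** The plan intends a split by compartment. Objectives 2.2.3 and 2.2.4 and the Study Summary pair RECIST 1.1 with soft tissue and PCWG3 with bone. Section 6.1.4 has bone read by bone scan under PCWG3. The heading of 6.1.7 takes bone out of the non-target rule ("excluding bone lesions, which will be assessed as below"). Section 6.1.8 then sets the bone rule: "Appearance of two or more new skeletal lesions that is confirmed on a repeat scan".

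Other text does not repeat the split:

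- The note to target-lesion progression in 6.1.6 reads "the appearance of one or more new lesions is also considered progressions", with no word on bone or confirmation.
- The last row of each table in 6.1.9 (measurable and non-measurable disease) gives PD for any new lesion. What counts as a new lesion is left to the RECIST publication.
- Section 6.1.2 puts "Bone lesions, leptomeningeal disease, ascites, pleural/pericardial effusions" among non-measurable disease, and 6.1.1 sends patients whose lesions are evaluable but not measurable to non-target assessment.
- Section 6.3.4 runs rPFS from first dose to "the time to radiologic progression by RECIST 1.1 or PCWG3 bone criteria", or death, and cites 10.1.6-108. Section 10.1 is the sample-size section and has no such subsections.
- Section 6.3.3 defines a responder by CR or PR (citing 10.1.6 and 10.1.7) together with no confirmed progression on bone scan (citing 10.1.8).

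Within 6.1.8, the stable-or-improved class "requires that no new lesions appear on radionuclide bone scan or that new pain has not developed" in an area already visualized.

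**The concern.** Two operative rules give different answers for the same scan. A patient whose only change is one new bone lesion has progressed under the 6.1.6 note and the 6.1.9 tables, and has not progressed under 6.1.8. The rPFS definition accepts either criterion without saying which applies to bone, and its cross-reference cannot settle the matter because it points nowhere. The trial runs at three centers, so the answer could depend on which section the person scoring the scan opens. At stake are whether some rPFS events are counted, when they are dated and, more narrowly, some best responses. The class definitions in 6.1.8 do not resolve the doubt, because under one reading they overlap and under the other they leave a single new lesion unclassified.

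**Working it through.** No figure in the plan depends on this point, so there is nothing to reproduce. The check sets the passages side by side and then sizes one call.

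**1. The rules for a new lesion**

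| Section | New lesions needed | Confirmation | Bone excluded? |
|---|---|---|---|
| 6.1.6 note | 1 | none stated | not stated |
| 6.1.7 | 1 | later confirmation only for clear non-target-only progression | yes, in the heading |
| 6.1.8 | 2 | repeat scan | bone only |
| 6.1.9, both tables, last row | 1 | none stated | not stated |

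**2. Routes into the endpoints.** The references in 6.3.4 most plausibly mean 6.1.6 to 6.1.8. On that reading 6.1.9 is not cited, and the route for a single bone lesion into rPFS is the 6.1.6 note. For ORR, 6.3.3 states the confirmed-bone condition itself. A single bone lesion can matter only because 6.3.3 uses best response, and best overall response is defined in 6.1.9. Even then, a PR recorded at an earlier scan stands, since 6.1.9 takes the best result up to progression.

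**3. Timing.** Scheduled scans fall at month 2, then 2 + 3 = 5, 5 + 3 = 8 and 8 + 3 = 11. One new bone lesion at month 2 is an event at 2 months under 6.1.6, and no event at that scan under 6.1.8. If two new lesions at month 2 are confirmed only at the next scheduled scan, the event is dated at 2 or at 5 months, because neither 6.1.8 nor 6.3.4 says which scan counts.

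**4. Size for rPFS.** Assume all 25 planned patients are at risk with no censoring. One call moves the Kaplan-Meier estimate at that scan by 1/25 = 4 percentage points. With stage one only it is 1/15 = 6.7 points. As an extreme illustration using scheduled scans only, 12 events at month 2 leave 13/25 = 0.52, so the median is at the next event, month 5 at the next scheduled scan if nothing happens between. A 13th event leaves 12/25 = 0.48 and a median of 2 months.

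**5. Size for ORR, if 6.1.9 is used.** The number with measurable disease is not given; assume 10 to 25. One reclassified responder moves ORR by 1/10 = 10 points down to 1/25 = 4 points. For example, 2/10 = 20% (90% exact CI 3.7 to 50.7%) becomes 1/10 = 10% (0.5 to 39.4%).

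**6. Classes within 6.1.8**

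| Bone scan | New pain | Literal reading with the *or* | Only the no-new-lesion limb |
|---|---|---|---|
| 1 new | no | stable | neither class |
| 1 new | yes | neither class | neither class |
| 2 or more, unconfirmed | no | stable | neither class |
| 2 or more, confirmed | no | stable and progression | progression |

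**The case against.** The strongest reply is that the intent is clear. The compartment labels appear in the objectives, the Study Summary and 6.1.4 as well as in the 6.1.7 heading, so the *or* in 6.3.4 is naturally read as soft tissue by RECIST or bone by PCWG3. The non-target column in 6.1.9 takes its statuses from 6.1.7, which excludes bone. The list in 6.1.2 is generic RECIST text. These points stand. They show what was meant and so support the correction, but they do not change the 6.1.6 note or the new-lesion rows.

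A reader might infer more than the text supports:

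- *That the two-lesion rule is bypassed for both rPFS and ORR.* For rPFS the text permits this reading but does not require it. For ORR, 6.3.3 contains the confirmed-bone condition, and patients with bone disease only never enter the ORR denominator.
- *That each affected patient shifts by at least 3 months, or that everyone with bone disease is exposed.* Scans may be done whenever clinically indicated, and 6.1.8 asks for a repeat scan without tying it to the next scheduled one. Only patients who develop a new bone lesion are exposed.
- *That early calls cost PSA data and so reach the primary endpoint.* Section 4.5 sets no stop for a single bone lesion, and PSA is drawn at End of Treatment.

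The missing dating rule is a gap in detail: 6.1.4 relies on PCWG3 and PCCTC forms, which may supply one but are not part of the documents.

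**Conclusion.** The contradiction is real and confined to secondary endpoints. Read literally, one unconfirmed new bone lesion is an rPFS event under 6.1.6 and 6.1.9 and not under 6.1.8, and 6.3.4 does not decide between them. Each such call is worth about 4 percentage points on the rPFS curve with 25 patients at risk. How many calls will arise cannot be said, because the documents give no rate of new bone lesions. The effect on ORR is conditional on using 6.1.9 for best response. The overlap and gap within 6.1.8 are a separate defect that holds whichever section governs. The conclusion assumes that the 10.1.x references mean 6.1.6 to 6.1.8. If 6.1.9 was also meant, the rPFS conflict is the same and the ORR conflict is stronger. The two-stage rule on PSA response is untouched.

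**What to change.** - **6.1.6 and both 6.1.9 tables:** state that new lesions and non-target lesions mean non-bone lesions, and that bone is judged only by 6.1.8.
- **6.3.4:** define the event as soft-tissue progression by RECIST 1.1, confirmed bone progression by 6.1.8, or death, and state which scan dates a confirmed bone progression.
- **6.3.3 and 6.3.4:** correct the 10.1.x references to 6.1.6 to 6.1.8.
- **6.1.8:** reword so that the classes do not overlap, and class a single or unconfirmed new lesion as not progression for endpoint purposes. Swapping *or* for *and* is not enough, because new pain without a new lesion would then fall in neither class.
- **4.5:** it refers to both PCWG3 and RECIST progression, so it must be reconciled with the amended definitions. What that means for treatment is for the sponsor and investigators to settle.

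The cost is wording, with no added visits or scans. The downside is that a few single-lesion calls will be dated later or not counted. The text should be settled before scans are scored for analysis.

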**6.1.9 Evaluation of best overall response by RECIST V1.1**

The best overall response is the best response recorded from the start of the treatment until disease progression/recurrence (taking as reference for progressive disease the smallest measurements recorded since the treatment started). The patient's best response assignment will depend on the achievement of both measurement and confirmation criteria.

For Patients with Measurable Disease (i.e., Target Disease)

Target Lesions	Non-Target Lesions	New Lesions	Overall Response
CR	CR	No	CR
CR	Non- CR/Non-PD	No	PR
CR	Not evaluated	No	PR
PR	Non- CR/Non-PD/not evaluated	No	PR

SD	Non- CR/Non-PD/not evaluated	No	SD	
PD	Any		PD	
Any	PD***		PD	no prior SD, PR or CR
Any	Any	Yes	PD	

\* See RECIST 1.1 manuscript for further details on what is evidence of a new lesion.  
 \*\*\* In exceptional circumstances, unequivocal progression in non-target lesions may be accepted as disease progression.

Note: Patients with a global deterioration of health status requiring discontinuation of treatment without objective evidence of disease progression at that time should be reported as "symptomatic deterioration." Every effort should be made to document the objective progression even after discontinuation of treatment.

**For Patients with Non -Measurable Disease (i.e., Non Target Disease)**

Non-Target Lesions	New Lesions	Overall Response
CR	No	CR
Non-CR/non-PD	No	Non-CR/non-PD*
Not all evaluated	No	not evaluated
Unequivocal PD	Yes or No	PD
Any	Yes	PD

\* 'Non-CR/non-PD' is preferred over 'stable disease' for non-target disease since SD is increasingly used as an endpoint for assessment of efficacy in some trials so to assign this category when no lesions can be measured is not advised

## 6.2 Assessment of primary endpoint

The assessment of the primary endpoint of confirmed PSA response rate is defined as the proportion of subjects who received at least 1 dose of the study drug achieving a post-treatment PSA partial response or complete response as defined by PSA response criteria in section 6.1.5

## 6.3 Assessment of secondary endpoints

- 6.3.1 The safety and tolerability of sEphB4-HSA in patients with mCRPC will be assessed according to NCI CTCAE v 5.0 and reported by the toxicity, severity, and attribution will be recorded for each cycle.
- 6.3.2 The time to PSA progression will be assessed by calculating the interval from administration of the first dose of drug on cycle 1 day 1 to PSA progression. PSA progression is defined by the criteria in section 6.1.5 PSA will be assessed every odd cycle.
- 6.3.3 The overall response rate will be the proportion of patients with measurable disease who received at least 1 dose of the study drug and as their best response achieved a partial or complete response (responder). A subject will be classified as a responder if the RECIST 1.1 criteria for a CR or PR are satisfied (see 10.1.6 and 10.1.7) as well as the absence of confirmed progression on bone scan assessed by PCWG3 (see 10.1.8) at any time up to and including the defined analysis cut-off point. Disease evaluation will be assessed by imaging at baseline and 2 months after starting therapy; thereafter, imaging will be conducted every 3 months. After 1 year, imaging can be done every 4 months for patients with stable disease or better. Scans may also be conducted at any time, if clinically indicated.

6.3.4 The time to radiologic progression (rPFS) will be assessed by calculating the interval from administration of the first dose of drug on cycle 1 day 1 to the time to radiologic progression by RECIST 1.1 or PCWG3 bone criteria (10.1.6-108) or death from any cause. Imaging will occur at baseline and 2 months after starting therapy; thereafter, imaging will be conducted every 3 months. After 1 year, imaging can be done every 4 months for patients with stable disease or better. Scans may also be conducted at any time, if clinically indicated.

#### **6.4 Exploratory Endpoints**

- 6.4.1 EphB4 and ephrinB2 expression will be assessed by IHC staining of primary and/or metastatic site (recent archival specimen or new biopsy). EphB4 and other biomarker abnormalities will be assessed by analyzing genomic alterations that are described in the results of molecular analysis reports that are obtained from standard of care tests (i.e., results from standard of care NGS testing/ genetic testing/ genomic testing, etc.)
- 6.4.2 Analysis of cfDNA for abnormalities in PI3K pathway, MYC or TP53.
- 6.4.3 IHC for CD3, CD4, CD8, and NK cell markers to characterize the immune infiltrate in tumor specimen.

### **7 ADVERSE EVENTS**

This study will be conducted in compliance with the Data Safety Monitoring Plan (DSMP) of the Robert H. Lurie Comprehensive Cancer Center of Northwestern University. The level of risk attributed to this study requires High Risk Monitoring, as outlined in the [DSMP](#). In addition, the study will abide by all safety reporting regulations, as set forth in the Code of Federal Regulations.

#### **7.1 Adverse Event Monitoring**

Adverse event data collection and reporting, which are required as part of every clinical trial, are done to ensure the safety of subjects enrolled in the studies as well as those who will enroll in future studies using similar agents. Adverse events are reported in a routine manner at scheduled times during a trial (see Section 5 for time points). In addition, certain adverse events must be reported in an expedited manner to allow for optimal monitoring and patient safety and care.

All patients experiencing an adverse event, regardless of its relationship to study drug, will be followed until:

- the adverse event resolves or the symptoms or signs that constitute the adverse event return to baseline;
- any abnormal laboratory values have returned to baseline;
- there is a satisfactory explanation other than the study drug for the changes observed; or
- death.

#### **7.2 Definitions & Descriptions**

##### **7.2.1 Adverse Event**

An adverse event (AE) is any untoward medical occurrence in a patient receiving study treatment and which does not necessarily have a causal relationship with this treatment. An AE can therefore be any unfavorable and unintended sign (including an abnormal laboratory finding), symptom, or disease temporally associated with the use of an experimental intervention, whether or not related to the intervention.

Recording of AEs should be done in a concise manner using standard, acceptable medical terms. In general, AEs are not procedures or measurements, but should reflect the reason for the procedure or the diagnosis based on the abnormal measurement. Preexisting conditions that worsen in severity or frequency during the

study should also be recorded (a preexisting condition that does not worsen is not an AE). Further, a procedure or surgery is not an AE; rather, the event leading to the procedure or surgery is considered an AE.

If a specific medical diagnosis has been made, that diagnosis or syndrome should be recorded as the AE whenever possible. However, a complete description of the signs, symptoms and investigations which led to the diagnosis should be provided. For example, if clinically significant elevations of liver function tests are known to be secondary to hepatitis, "hepatitis" and not "elevated liver function tests" should be recorded. If the cause is not known, the abnormal test or finding should be recorded as an AE, using appropriate medical terminology (e.g/ thrombocytopenia, peripheral edema, QT prolongation).

#### 7.2.2 Severity of AEs

All non-hematologic adverse events will be graded according to the NCI Common Terminology Criteria for Adverse Events (CTCAE) version 5.0. The CTCAE v 5.0 is available at

[https://ctep.cancer.gov/protocoldevelopment/electronic\\_applications/ctc.htm](https://ctep.cancer.gov/protocoldevelopment/electronic_applications/ctc.htm)

If no CTCAE grading is available, the severity of an AE is graded as follows:

Grade 1: Mild; asymptomatic or mild symptoms; clinical or diagnostic observations only; intervention not indicated.

Grade 2: Moderate; minimal, local or noninvasive intervention indicated; limiting age-appropriate instrumental activities of daily living\*.

Grade 3: Severe or medically significant but not immediately life-threatening; hospitalization or prolongation of hospitalization indicated; disabling; limiting self care activities of daily living\*\*.

Grade 4: Life-threatening consequences; urgent intervention indicated.

Grade 5: Death related to AE

\*Instrumental activities of daily living refer to preparing meals, shopping for groceries or clothes, using the telephone, managing money, etc.

\*\*Self care activities of daily living refer to bathing, dressing and undressing, feeding self, using the toilet, taking medications, and not bedridden.

